## 5 PROCEDURES

**5.1 Study procedures.** Using lay language, provide a complete description of the study procedures, including the sequence, intervention or manipulation (if any), drug dosing information (if any), use of records, time required, and setting/location. If it is available and you think it would be helpful to the IRB: Upload a study flow sheet or table to the **Supporting Documents SmartForm** in **Zipline**.

*For studies comparing standards of care: It is important to accurately identify the research procedures. See UW IRB [POLICY: Risks of Harm from Standard Care](#) and the draft guidance from the federal Office of Human Research Protections, ["Guidance on Disclosing Reasonably Foreseeable Risks in Research Evaluating Standards of Care"](#), October 20, 2014.*

Aim 1:  
[redacted]

Aim 2:

Once a local health department has been recruited to participate in the study, they will be randomized to one of two conditions for the trial: 1) standard training and technical assistance or 2) standard training plus enhanced technical assistance.

Briefly, local health department staff will be trained to deliver the *Connect to Wellness* intervention to worksites that they recruit. In the Assessment phase, staff will measure current worksite implementation of physical activity, nutrition, cancer screening, and tobacco cessation evidence-based interventions (with the Baseline Employer Assessment Survey). [redacted] During the Implementation phase (months 3-12), the worksite begins adopting the recommended evidence-based intervention policies and programs and promoting them to workers. At the conclusion of the Implementation phase (month 12), the local health department staff will re-administer the Employer Assessment Survey. After this 12-month period, worksites are able to contact the local health department for technical assistance; the health department may also periodically contact worksites with study updates or to provide relevant materials or offer implementation support.

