Once a local health department is assigned to the standard arm, a member of the research team will contact staff to arrange dates for the training sessions, ship materials for the worksites (e.g. toolkits), and provide a detailed *Connect to Wellness* protocol to use with worksites that they recruit. The research team will e-mail information about the *Connect to Wellness* training website and ensure that staff are able to register. Local health department staff will attend three online training webinars, each lasting two hours, in groups of five. (Note: Five refers to the number of local health departments represented in each group). These real-time webinars will be supported by Zoom software. Topics covered in this training will include an introduction to *Connect to Wellness*, methods for recruiting worksites, how to administer the Employer Assessment Survey, how to create and deliver the recommendations report, an overview of intervention implementation and programming, how to track (e.g. their interactions with worksites, time spent on project), and discussion of common barriers and solutions. At the conclusion of the third training webinar, we will work with each group of local health departments to identify a time for monthly group technical assistance calls, where staff will have time to share lessons learned and success stories. Features will be added to the *Connect to Wellness* website to encourage communication between members of each five-local health department group, such as discussion forums and instant chat.

Local health departments assigned to the enhanced arm will undergo initial and online training procedures as described above. Each group will also have a monthly technical assistance call and access to the online peer-communication tools described above. In addition, local health departments in this arm will have one-on-one telephone access to a member of our research team. They can call her for advice; she will proactively contact each local health department in this arm monthly if they have not contacted her during that time. Enhanced support will be given for 24 months, the same length as the study period for this aim.

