	No
	Yes

→ If yes, briefly describe the urgency or deadline as well as the reason for it.

**1.5 Objectives** Using lay language, describe the purpose, specific aims, or objectives that will be met by this specific project. If hypotheses are being tested, describe them. You will be asked to describe the specific procedures in a later section.

If your application involves the use of a HUD "humanitarian" device: describe whether the use is for "on-label" clinical patient care, "off-label" clinical patient care, and/or research (collecting safety and/or effectiveness data).

The primary goals of this study are to (a) scale up *Connect to Wellness* by training staff in local health departments across the United States to deliver *Connect to Wellness* to small worksites in their communities, and (b) conduct a trial comparing the effectiveness and costs of two different implementation strategies.

It has been previously proven that *Connect to Wellness* is effective. Our objective now is to determine the best way to implement it. Although the local health departments will be involved in collecting identifiable data, they are not engaged in the research because we are not testing the efficacy of *Connect to Wellness*.

Study goals will be achieved through three aims:

Aim 1: Conduct formative research (interviews and focus groups) with state and local health departments

Aim 2: Test two different implementation strategies with local health departments: 1) standard *Connect to Wellness* training and technical assistance and 2) standard *Connect to Wellness* training plus enhanced technical assistance

Aim 3: Measure the costs of each implementation strategy

**1.6 Study design.** Provide a one-sentence description of the general study design and/or type of methodology.

*Your answer will help HSD in assigning applications to reviewers and in managing workload. Examples: a longitudinal observational study; a double-blind, placebo-controlled randomized study; ethnographic interviews; web scraping from a convenience sample of blogs; medical record review; coordinating center for a multi-site study.*

Aim 1 activities are qualitative. We will conduct semi-structured interviews and focus groups with participants via online and telephone methods.

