## 5 PROCEDURES

**5.1 Study procedures.** Using lay language, provide a complete description of the study procedures, including the sequence, intervention or manipulation (if any), drug dosing information (if any), use of records, time required, and setting/location. If it is available and you think it would be helpful to the IRB: Upload a study flow sheet or table to the **Supporting Documents SmartForm** in **Zipline**.

*For studies comparing standards of care: It is important to accurately identify the research procedures. See UW IRB [POLICY: Risks of Harm from Standard Care](#) and the draft guidance from the federal Office of Human Research Protections, ["Guidance on Disclosing Reasonably Foreseeable Risks in Research Evaluating Standards of Care"](#), October 20, 2014.*

Aim 1:  
[redacted]

Aim 2:

Once a local health department has been recruited to participate in the study, they will be randomized to one of two conditions for the trial: 1) standard training and technical assistance or 2) standard training plus enhanced technical assistance.

Briefly, local health department staff will be trained to deliver the *Connect to Wellness* intervention to worksites that they recruit. In the Assessment phase, staff will measure current worksite implementation of physical activity, nutrition, cancer screening, and tobacco cessation evidence-based interventions (with the Baseline Employer Assessment Survey). [redacted] At the conclusion of the Implementation phase (month 12), the local health department staff will re-administer the Employer Assessment Survey. After this 12-month period, worksites are able to contact the local health department for technical assistance; the health department may also periodically contact worksites with study updates or to provide relevant materials or offer implementation support.

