Study Identification

Unique protocol identification number: STUDY00004627

Brief Title: Training LHD's to disseminate evidence-based interventions to small work sites

Official Title: Training Local Health Departments to Disseminate Evidence-Based Interventions to Small and Low-Wage Worksites

Secondary IDs: 2R01CA160217 [U.S. NIH Grant/Contract Award Number]
NCI-2021-02876 [Registry ID: CTRP (Clinical Trial Reporting Program)]
RG1121453 [Fred Hutch/University of Washington Cancer Consortium]

Document date: June 28th, 2017

This document includes the statistical analysis plan excerpted from our grant proposal. We completed this text on the above date.

Statistical analysis plan

To test whether LHDs in the enhanced arm recruit more worksites than LHDs in the standard arm, we will use a generalized linear model with log link. Robust standard error will be performed to obtain valid test results, since we expect the number of worksites recruited to be overdispersed relative to the Poisson distribution. We will perform a secondary analysis to test whether the rate of recruitment increases over time and whether such an increase is modified by treatment status. To study the time effects, we will analyze the number of worksite recruitments in 6-month intervals. The estimation will be implemented using a generalized estimating equation with an autoregressive working correlation matrix of order 1. Robust standard error will be performed to obtain valid test results of correlated outcome data. We will use linear models to study the worksite implementation score. Since worksites are nested within LHDs, we will implement the estimation using generalized estimating equation with robust standard error.

Power analysis. Our first primary outcome is the number of worksites recruited by each LHD during the study period (24 months). Based on power analysis using the Washington State pilot data, we propose a sample size of 40 LHDs (20 per arm) for this study. The mean number of worksites recruited over a 12-month period was 8.4 (sd=4.4). The proposed design will have at least 80% power to detect a mean difference of 2.6 worksites per year between the two arms. Our second primary outcome is the worksite implementation score, collected 12 months after the initial delivery of *Connect to Wellness*. Based on the preliminary results of the parent project, our design has at least 80% power to detect a 6% difference in implementation scores between the two intervention groups.

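### The month-12 implementation score is compared only among worksites recruited after randomisation, so the arm difference needs baseline adjustment and a narrower interpretation

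*SAP*

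**What the plan says.** The unit of randomisation is the LHD. Protocol section 5.1 states: "Once a local health department has been recruited to participate in the study, they will be randomized to one of two conditions". Training follows assignment and covers "methods for recruiting worksites". Staff then deliver the "intervention to worksites that they recruit". The arms differ in that only the enhanced arm has "one-on-one telephone access to a member of our research team", for 24 months. Section 10.6 answers the un-blinding question as not applicable. Section 2.2 recommends worksites of 20 to 200 employees to LHD staff but does not require them. The same staff give the Employer Assessment Survey at baseline and again at month 12.

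The SAP's first primary analysis is introduced as "To test whether LHDs in the enhanced arm recruit more worksites than LHDs in the standard arm". On the second it says: "Our second primary outcome is the worksite implementation score, collected 12 months after the initial delivery of" the programme. The model is given as: "We will use linear models to study the worksite implementation score. Since worksites are nested within LHDs", after which it specifies GEE with robust standard error. It names no baseline term, no worksite covariates, no rule for a missing month-12 survey, no treatment of an LHD without scored worksites, and no sensitivity analysis.

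**The concern.** A score exists only for a worksite that was recruited and was still there to be surveyed 12 months after delivery began. Which worksites those are is decided after assignment, by staff whose recruiting the enhanced support is expected to change. If the first primary hypothesis is true, the set of worksites behind the second primary outcome differs by arm. Equal numbers would not guarantee comparable worksites either. Clustering by LHD gives a valid standard error for the difference between two recruited groups. It does not make those groups comparable.

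The stated goal in Protocol section 1.5 is to "conduct a trial comparing the effectiveness and costs of two different implementation strategies". A score difference read as the effect of the strategy on implementation could partly reflect which worksites were brought in. The SAP does not say how to read the score if it and the recruitment count point in different directions.

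**Working it through.** **Inputs from the SAP.** Pilot recruitment is 8.4 worksites per 12 months (SD 4.4). The target recruitment difference is 2.6 per year, with 20 LHDs per arm. The score target is 6%, with at least 80% power. **Assumptions.** The pilot mean stands for the standard arm; 6% means 6 points; tests are two-sided at 5%; each worksite counts equally (the SAP names no working correlation for the score); apart from the extra worksites, the arms recruit alike.

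**1. The plan's own power figure.** It cannot be reproduced, because the score SD, intracluster correlation (ICC) and number of scored worksites per LHD (m) are not given. Solving backwards, with n_eff = 20m/(1 + (m − 1)ICC), the largest SD that gives 80% power is 6/(2.80 × √(2/n_eff)). For m = 8.4 and ICC = 0.05, n_eff = 168/1.37 = 122.6 and the SD is 16.8. Over m = 5 to 16.8 and ICC = 0.01 to 0.30 the range is 10.2 to 25.8. The figure is neither confirmed nor refuted, so it is taken as given below: standard error = 6/2.80 = 2.14 points.

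**2. Share of extra worksites.** Enhanced arm: 8.4 + 2.6 = 11.0 per year. Share: 2.6/11.0 = 0.236.

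**3. Shift in the arm difference.** If the extra worksites score d points below the rest, the shift is −0.236d. Power is Φ(observed difference/2.14 − 1.96).

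| d (points lower) | Shift | True 6 appears as | Power | True 0: chance of a significant result |
|---|---|---|---|---|
| 5 | −1.2 | 4.8 | 61% | 9% |
| 10 | −2.4 | 3.6 | 40% | 20% |
| 20 | −4.7 | 1.3 | 9% | 60% |
| 25.4 (= 6/0.236) | −6.0 | 0 | 2.5% | 80% |

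If the extra worksites score higher, the signs reverse: at 10 points higher, a true 6 appears as 8.4 and a true 0 as 2.4.

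**4. What baseline adjustment recovers.** A cluster simulation (assumed SD 20, ICC 0.05, true effect 6, baseline carrying the whole gap) gave unadjusted estimates of 3.6, 1.3 and −0.1 at d = 10, 20 and 25.4. Adjusted for baseline, they were 6.0, 6.0 and 5.9. This is the favourable case. If the extra worksites start level but respond less, a baseline term does not help. Suppose comparable worksites gain 10 points and the extra ones gain 5. Over 24 months the enhanced arm totals 16.8 × 10 + 5.2 × 5 = 194 per LHD, against 168 in the standard arm. Its mean gain is 194/22 = 8.8, against 10.0.

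**5. Power of an LHD-level total.** In that example the difference is 194 − 168 = 26. Use count variability alone at 10 points per worksite. The 24-month count SD is 4.4√2 = 6.2 (independent years) to 8.8 (perfectly correlated years), so the total has SD 62 to 88. Standard error = SD × √(2/20) = 20 to 28, and power is 26% down to 15%. A difference of 2.80 × SE, about 55 to 78, is needed for 80%. If only first-year recruits count, the difference is 2.6 × 5 = 13, the SD 44 and the standard error 13.9, again 15%.

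**The case against.** Several counter-arguments have force.

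- A reader might infer that the trial has no outcome protected by randomisation. That is wrong. The recruitment count is defined for every randomised LHD, zeros included. Protocol section 5.2 also collects LHD-level completion counts and adoption, implementation and maintenance items at 12 and 24 months, although the SAP gives no model for them.
- A reader might infer that the extra worksites will be harder ones and that the enhanced arm will be penalised. The documents neither support nor exclude this. Both arms share the 15-worksite commitment, the size recommendation and the recruitment training, and closer support might equally bring in keener worksites.
- A reader might conclude that the effectiveness statement should rest on a summed LHD total. The documents do not support that. Keeping reach and implementation apart is a legitimate choice in a hybrid type III trial, opposite results would be informative, and the sum largely repeats the recruitment count with little power.
- LHDs that recruit nobody should be rare. A negative binomial with 24-month mean 16.8 and SD 8.8 has p = 16.8/77.44 = 0.217 and r = 16.8²/(77.44 − 16.8) = 4.65. So P(0) = 0.217^4.65 = 0.0008, or 0.03 of 40 LHDs. This leaves out LHD withdrawal and LHDs whose worksites all miss month 12.
- The phrase linear models does not rule out a baseline term.

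The structural point survives all of these. The scored worksites are selected after randomisation, and the SAP specifies no step for it.

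**Conclusion.** The concern holds in a limited form. As planned, the second primary analysis estimates a difference among recruited worksites that have a month-12 survey, not a randomisation-protected effect of the strategy on implementation. At the SAP's recruitment difference the distortion is 0.24 points per point of score gap, in either direction: 1.2 points for a gap of 5 and 2.4 for a gap of 10. Cancelling the 6-point target needs a gap of about 25 points, so dilution and lost power are more plausible than reversal. The gap is an assumption, and the documents give no figure for it. The SAP should say what the score result means and use the baseline data. Neither primary outcome needs replacing.

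**What to change.** 1. Add the worksite's baseline Employer Assessment score to the GEE model for the month-12 score. Report baseline score and number of employees of recruited worksites by arm. Baseline scores are already collected. Protocol section 5.2 does not list worksite size, so confirm that it is recorded.
2. State in the SAP that the score result applies to recruited worksites with a month-12 survey and is interpreted alongside the recruitment outcome.
3. Add a supportive LHD-level analysis over all 40 randomised LHDs: the sum of month-12 minus baseline score across an LHD's worksites, with zero for an LHD that has none. Compare arms by a linear model with robust standard error. Limit it to worksites recruited early enough to reach month 12 within data collection. Otherwise second-year recruits in a 24-month study could enter as zeros. For missing month-12 surveys, specify a sensitivity analysis and do not rely on zero alone. Zero is not reliably conservative: it rates a lost worksite above one that stayed and worsened, and unequal loss by arm can bias either way.

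The cost is SAP wording and a little extra analysis, mostly on data already planned. The LHD total has low power (about 15% to 26% in the example above) and partly repeats the recruitment outcome, so it should be labelled supportive. Baseline adjustment removes only the differences that baseline captures.

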**2.2 Inclusion and exclusion criteria.**

**a. Inclusion criteria.** Describe the specific criteria you will use to decide who will be included in your study from among interested or potential subjects. Define any technical terms in lay language.

Aim 1:  
[redacted]

Aims 2/3:

Local health departments in the 50 states and District of Columbia will be eligible to participate in the randomized controlled trial. Additional eligibility criteria include willingness to support one or more staff members to participate in *Connect to Wellness* training and the project for two years, and to have these staff recruit 15 or more worksites for *Connect to Wellness* over 24 months. We will recommend to local health department staff that they focus on recruiting worksites with 20-200 employees (i.e. worksites with fewer resources for workplace health promotion, and for which the strongest evidence for the effectiveness of *Connect to Wellness* is present). The worksite representatives will need to be able to speak and read English, and be knowledgeable about health and wellness at the worksite (e.g. HR manager). We expect that representatives will be at least 18 years of age or older.

**b. Exclusion criteria.** Describe the specific criteria you will use to decide who will be excluded from your study from subjects who meet the inclusion criteria listed above. Define any technical terms in lay language.

Aim 1:  
[redacted]

Aims 2/3:

Local health departments who are not able to support staff to participate in *Connect to Wellness* will be excluded from the study.

**2.3 Prisoners.** IRB approval is required in order to include prisoners in research, even when prisoners are not an intended target population.

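### Both primary tests rest on an unspecified robust standard error with 20 LHDs per arm; the ordinary uncorrected form, which the SAP permits, would reject a true null about 6.4–7.2% of the time at an assumed two-sided 5%

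*SAP*

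**What the plan says.** The SAP (Statistical analysis plan) compares recruitment between arms with a generalized linear model with log link, one count per LHD. It gives the reason for the variance choice: "Robust standard error will be performed to obtain valid test results, since we expect the number of worksites recruited to be overdispersed". For the worksite implementation score it uses a linear model, and: "Since worksites are nested within LHDs, we will implement the estimation using generalized estimating equation with robust standard error". In that model the LHDs are the clusters.

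On size, the SAP (Power analysis) says: "we propose a sample size of 40 LHDs (20 per arm) for this study".

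Neither the SAP nor the protocol says which robust variance is meant, whether it is corrected for few clusters, whether the test refers to a normal or a t distribution and on what degrees of freedom, or what alpha and sidedness apply. A working correlation is named for the secondary analysis of 6-month intervals (autoregressive, order 1) but not for the score model.

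**The concern.** The uncorrected sandwich estimator is valid as the number of independent units grows. With 20 per arm it is biased low for two reasons that add up. Squared deviations in each arm are in effect divided by 20 rather than 19, and a normal reference ignores the fact that the variance itself is estimated from only 40 units. Standard errors and intervals are then too small, and both primary tests lean towards false positives.

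The SAP relies on the robust standard error to make the tests valid. An analyst who followed the text literally with an ordinary uncorrected robust variance would not quite achieve that. Because nothing is specified, several variants with different error rates all comply with the plan, and the choice could be made after the data are seen.

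**Working it through.** **The plan's own figure.** The documents give no type I error to reproduce. The nearest figure is at least 80% power for a difference of 2.6 worksites per year, and it cannot be checked without alpha, sidedness and a 24-month SD. With a 24-month difference of 2 × 2.6 = 5.2, an SD of 4.4 × √2 = 6.22 (independent years, assumed) and 20 per arm, a normal-approximation comparison of means gives 75% two-sided and 84% one-sided. The point below does not rest on this figure.

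**Inputs from the documents.** 20 LHDs per arm; pilot mean 8.4 and SD 4.4 worksites over 12 months; 24-month recruitment period; the protocol's recruitment commitment (section 2.2), "to have these staff recruit 15 or more worksites for" the intervention.

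**Assumptions.** Two-sided 5%; all 40 LHDs analysed; LHDs independent. The ICC of the score is not given, so 0.01, 0.05, 0.10 and 0.20 are used. The 24-month SD of the count is not given, so 6.2 (independent years), 7.8 (pilot dispersion carried to the larger mean) and 8.8 (fully correlated years) are used.

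**1. Equal cluster sizes, exact for normal data.** The uncorrected statistic is distributed as t38 × √(20/19). With critical value 1.960:

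2 × P(t38 > 1.960 × √(19/20)) = 2 × P(t38 > 1.910) = 6.37%.

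No ICC or SD enters. Other choices by the same route:

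| Variance | Reference | Type I error |
|---|---|---|
| uncorrected | normal | 6.37% |
| × 40/39 | normal | 6.05% |
| × 20/19 | normal | 5.74% |
| uncorrected | t38 | 5.58% |
| × 20/19 | t38 | 5.00% |

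With 16 LHDs per arm, the first row becomes 2 × P(t30 > 1.960 × √(15/16)) = 6.7%.

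**2. Recruitment count.** With arm as the only covariate, the uncorrected variance of the log rate ratio is the sum over arms of Σ(y − ȳ)² / (n²ȳ²). The Kauermann–Carroll correction multiplies each arm's term by n/(n − 1), here 20/19. Simulation used negative binomial counts, 24-month mean 2 × 8.4 = 16.8, and 400,000 trials per setting:

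| Assumed SD | Uncorrected, normal | × 20/19, t38 |
|---|---|---|
| 6.2 | 6.49% | 5.11% |
| 7.8 | 6.52% | 5.12% |
| 8.8 | 6.62% | 5.25% |

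**3. Implementation score, unequal numbers of worksites per LHD.** Under an independence working correlation, each LHD adds [m(ȳ − μ̂)]² / N² to its arm's variance, where m is its number of worksites, ȳ its mean score, μ̂ the arm mean and N the arm's total worksites. Kauermann–Carroll divides this by 1 − m/N. Numbers of worksites per LHD, mean (SD), were:
- 8.4 (4.4), if only first-year recruits reach a 12-month score within 24 months.
- 15 (about 7.1). Here the recruitment commitment is used as a mean, which is an assumption. The SD comes from the pilot's negative binomial dispersion: 8.4² / (4.4² − 8.4) = 6.44, and √(15 + 15²/6.44) = 7.1.
- 16.8 (6.2, 7.8 or 8.8).

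With 200,000 trials per setting (Monte Carlo error about 0.06 points), across all settings:

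| Working correlation | Uncorrected, normal | Kauermann–Carroll, t38 |
|---|---|---|
| independence | 6.61–7.18% | 5.13–5.50% |
| exchangeable | 6.45–6.86% | 5.02–5.32% |

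**4. Interval width.** For the count, corrected to uncorrected is √(20/19) × 2.024/1.960 = 1.060, so the uncorrected interval is about 5.6% narrower than the corrected one (1 − 1/1.0597). For the score the ratio is 1.060–1.071, so 5.6–6.6% narrower.

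**5. Power.** With equal sizes and noncentrality 2.759 on t38, power is 80.0% uncorrected and 76.7% corrected.

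**6. One-sided 5%.** The recruitment test is worded directionally ("To test whether LHDs in the enhanced arm recruit more worksites than LHDs in the standard arm"). If one-sided 5% was meant, the uncorrected error is P(t38 > 1.645 × √(19/20)) = 5.9% with equal sizes.

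**The case against.** The strongest reply is that the SAP never says it will use the uncorrected form. A robust standard error can be a corrected one, and the text is by its own account an excerpt from a grant proposal, where such detail is often left out. This stands to the extent that the 6.4–7.2% is conditional. A reader might infer that the planned tests have inflated error; the documents support only that the plan allows it.

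A second reply is that the effect is small. This is also fair. The excess is 1.4 points with equal sizes, it leaves the estimates unbiased, and it matters only for a p-value near the threshold.

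Third, the upper figures belong to one test. The 7.2% and the 6.6% interval shortfall arise only for the score, under an independence working correlation with unequal cluster sizes and assumed ICCs. They should not be read across to the count, where the excess is about 1.5–1.6 points.

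Fourth, other corrections would serve. A Mancl–DeRouen type variance with t38 gave 4.3–5.0% for the score, so Kauermann–Carroll is an example and not the only acceptable choice.

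What remains is that the omission concerns both primary tests, no other section of either document fills it, and a literal reading of the plan leads to a test that misses its nominal level.

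**Conclusion.** The point holds in conditional form and should be fixed, although its size is modest. At an assumed two-sided 5%, with the uncorrected sandwich and a normal reference, type I error is 6.4% with equal cluster sizes, about 6.5–6.6% for the count and about 6.5–7.2% for the score with unequal sizes. Only the equal-size figure is free of assumptions about ICC and spread. All of the figures assume 40 LHDs analysed and independent LHDs; with fewer LHDs the excess grows.

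Two further inferences are tempting and are not made. The secondary AR(1) analysis also uses a robust standard error, but it has time and arm-by-time terms, and no error rate was derived for it here. Training is shared between LHDs (protocol, section 5.1: "Local health department staff will attend three online training webinars, each lasting two hours, in groups of five"), which might suggest correlation above the LHD level. The documents give no such correlation, so no inflation is claimed for it.

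**What to change.** In the SAP, state alpha and sidedness, and the working correlation for the score model. For both primary tests, specify a small-sample-corrected sandwich variance, for example Kauermann–Carroll, with a t reference on the number of LHDs analysed minus 2 degrees of freedom. That is 38 if all 40 contribute. It should be written as a rule and not as a fixed number, because LHD staff may decline to continue (protocol, section 8.2e) and an LHD with no scored worksite adds no cluster to the score model.

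For the count model with arm only, the correction amounts to multiplying each arm's variance term by n/(n − 1), with n the LHDs analysed in that arm. A single factor based on the total, such as 40/39, is too small.

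The change takes a sentence or two in the SAP and a standard software option or a few lines of code. It brings type I error to about 5.0–5.5%. Intervals become about 6% wider for the count and 6–7% wider for the score, and an effect with 80% power in the uncorrected test has about 77%. Design, recruitment and delivery do not change.
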